8.3 Exploratory Efficacy Analyses

The level of hepcidin at baseline, 12 and 24 weeks will be evaluated in relation to the response to treatment in order to observe the relationship between the basal levels of hepcidin with the fall in filtrate and the hemoglobin level. We will also observe the response of hepcidin levels to treatment with erythropoietin and finally we will see if there is any type of association between hepcidin levels and the subgroup of patients who do not respond to erythropoietin.

9 Safety Analyses

The following measures will be performed during the study to evaluate safety parameters:

- Vital signs: Determinations of pulse and blood pressure, every visit.
- Physical examination: A brief physical examination was carried out at the baseline visit (week 1).
- Electrocardiogram: An electrocardiogram was performed at the baseline visit (week 1).

Data will be summarized and comparison between treatment groups regarding these parameters at the beginning or at the end of the study will be evaluated.

9.1 Adverse Events

As safety objective, the incidence of adverse events and adverse reactions will be evaluated after 12 and 24 weeks of treatment, comparing patients treated with HEMAX PFS versus those treated with EPREX/ ERYPO®.

An AE shall be considered as treatment - emergent adverse event (TEAE), if it presents after the first dose administered of the investigational product or if, preexistent prior to the administration of the first dose, it worsens after the administration of the same.

All TEAEs will be presented summarized through the use of Tables, for each organ class and preferred term to denominate them. The Tables will present the number of patients for which events occurred, and the incidence rate, expressed as a percentage calculated on the number of patients from the entire population included in the safety FAS.

The TEAEs will be presented by causality (relationship with the study drug), intensity (mild, moderate, severe). Treatment - emergent events that are serious and that lead to treatment discontinuation will also be summarized using the preferred term and the class organ system involved.

In addition, and with focus on safety, the following will be discussed:

- Incidence of thromboembolic events (myocardial infarction, cerebrovascular accident, deep vein thrombosis and other thromboembolic events).
- Incidence of hypertension as TEAE.
- Blood pressure values at each visit.
- Complete baseline laboratory data and at week 12 and 24 visits,
- Antibody dosages, baseline and at weeks 12 and 24.

For safety analysis, descriptive statistics will be performed mainly to evaluate the incidence of adverse events and adverse reactions after 12 and 24 weeks of treatment.

When calculating the incidence of adverse events, or any sub-classification (e.g. by treatment) each subject will be counted all the times a repetitions of adverse events will be occurred and the denominator will be the total population size.

All the adverse events occurred during the study will be listed according to treatment group and severity. The frequency of adverse events by system and treatment group, expressed as amount of events/number of affected patients and the relationship with study drug will be summarized.

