9.4 EARLY TREATMENT TERMINATION

The termination visit should be performed in all patients that completed the study prematurely. Patients who decide not to continue with the visits must perform the termination visit before completion. A patient may leave or be excluded from the study due to the following reasons:

- Death.
- Adverse event that in the opinion of the investigator requires early withdrawal (specify principal AE in the AE form).
- Revocation of informed consent.
- At the request of the investigator or physician primarily responsible for the care of the patient.
- Due to major protocol violation that required discontinuation.
- Loss of follow - up, including the fact that patient does not return to the site.
- Positive pregnancy test at any time during the study.
- Patient transfusion or lack of response after 12 weeks of treatment.
- If after twelve weeks the hemoglobin did not increase during the titration phase by at least 1 g/dL from baseline, the patient will be withdrawn from the study.

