11.3 CONCOMITANT MEDICATIONS/ TREATMENT OF ANEMIA

Transfusions: Patients will be transfused according to the clinical judgment of the investigator, based on the patient's symptoms and not on a cutoff value of hemoglobin. The transfused patients will be withdrawn from the study for having reached a study endpoint.

Iron intake: All patients will receive concomitant treatment with iron orally to maintain the levels of transferrin saturation >20% according to the indications of the treating physicians. The intravenous iron is also permitted, according to the criterion of the treating physicians.

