16.3.1 Full Analysis Set (FAS)

The full data analysis group will consist of all patients enrolled in this study that have been randomized and who have received at least one dose of the study medication.

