16.6 SAFETY ANALYSIS

The evaluation of safety shall be carried out using the entire population (FAS) of data, making focus on adverse events (AE).

As primary safety objective, the incidence of adverse events and adverse reactions will be evaluated after 12 and 24 weeks of treatment, comparing patients treated with HEMAX PFS versus those treated with EPREX/ ERYPO®.

An AE shall be considered as treatment - emergent adverse event (TEAE), if it presents after the first dose administered of the investigational product or if, preexistent prior to the administration of the first dose, it worsens after the administration of the same.

All TEAEs will be presented summarized through the use of Tables, for each organ class and preferred term to denominate them. The Tables will present the number of patients for which events occurred, and the incidence rate, expressed as a percentage calculated on the number of patients from the entire population included in the safety FAS.

The TEAEs will be presented by causality (relationship with the study drug), intensity (mild, moderate, severe). Treatment - emergent events that are serious and that lead to treatment discontinuation will also be summarized using the preferred term and the class organ system involved.

In addition, and with focus on safety, the following will be discussed:

- Incidence of **thromboembolic events** (myocardial infarction, cerebrovascular accident, deep vein thrombosis and other thromboembolic events).

- Incidence of **hypertension** as TEAE.
- **Blood pressure** values at each visit.
- **Complete baseline laboratory data** and at week 12 and 24 visits,
- **Antibody dosages**, baseline and at weeks 12 and 24.

For safety analysis, descriptive statistics will be performed mainly to evaluate the incidence of adverse events and adverse reactions after 12 and 24 weeks of treatment and x2 test will be performed to compare the incidence of adverse events and adverse reactions of patients treated with HEMAX® PFS versus those treated with EPREX/ERYPO®.

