3.2.3 Endpoints

EFFICACY EVALUATION

The following parameters will be evaluated for treatment efficacy, according to the objectives defined by the protocol at each visit:

- Levels of hemoglobin and its variation at each visit, with intragroup and intergroup comparison

The primary efficacy assessment will be carried out through the levels of hemoglobin increase from baseline value to the mean value of the visits between week 8 and 12, comparing patients treated with HEMAX PFS versus those treated with EPREX/ ERYPO®.

- Percentage of responder patients, defined as the increase of Hb $\geq 1\text{g/ dl}$ without transfusion requirement.

Percentage of responder patients (increase of Hb $\geq 1\text{g/ dl}$) after 12 weeks of treatment, comparing patients treated with HEMAX PFS versus those treated with EPREX/ ERYPO®.

- Number and percentage of patients that require at least one transfusion.

Percentage of transfusion requirement after 12 weeks of treatment, comparing patients treated with HEMAX PFS versus those treated with EPREX/ ERYPO®.

- Intragroup efficacy of treatment with epoetin alfa

Increased levels of hemoglobin from baseline in each one of the intermediate visits until the week 12 visit.

- Intragroup efficacy of the change from the twice a week dosing during the titration phase to a weekly dosing during the maintenance phase.

Variation of the hemoglobin levels from week 12 to weeks 16, 20 and 24.

- Level of hepcidin at baseline, 12 and 24 weeks.

Relationship between the basal levels of hepcidin with the fall in filtrate and the hemoglobin level.

Response of hepcidin levels to treatment with erythropoietin

Association between hepcidin levels and the subgroup of patients who do not respond to erythropoietin.

SAFETY EVALUATION

- Adverse events:

Incidence of adverse events and adverse reactions will be evaluated after 12 and 24 weeks of treatment, comparing patients treated with HEMAX PFS versus those treated with EPREX/ ERYPO®.

In addition, and with focus on safety, the following will be discussed:

- Incidence of thromboembolic events (myocardial infarction, cerebrovascular accident, deep vein thrombosis and other thromboembolic events).
- Incidence of hypertension as TEAE.
- Blood pressure values at each visit.
- Complete baseline laboratory data and at week 12 and 24 visits,
- Antibody dosages, baseline and at weeks 12 and 24
- Vital signs: Determinations of pulse and blood pressure were recorded at every visit.

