6.2.2 Safety Population

- All subjects who received any study treatment

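### The 24-week adverse event comparison is a crude percentage of all treated patients, although follow-up for non-serious events depends on efficacy; exposure-adjusted measures should be added beside it

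*SAP*

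**What the plan says.** Comparing adverse event incidence between arms at 12 and 24 weeks is a primary objective (protocol 6.1, SAP 3.2.2). Protocol 16.6 says that "the incidence of adverse events and adverse reactions will be evaluated after 12 and 24 weeks of treatment".

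The denominator is fixed. SAP 9.1 and protocol 16.6 both give the TEAE rate as "expressed as a percentage calculated on the number of patients from the entire population included in the safety FAS". The SAP safety population is "All subjects who received any study treatment"; the protocol's full analysis set is patients who "have been randomized and who have received at least one dose of the study medication".

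Follow-up is not fixed. Protocol 9.4 lists "Patient transfusion or lack of response after 12 weeks of treatment" among the reasons for leaving the study. If haemoglobin has not risen by week 12 "by at least 1 g/dL from baseline, the patient will be withdrawn from the study". Protocol 11.3 adds: "The transfused patients will be withdrawn from the study for having reached a study endpoint". Only responders enter weeks 12 to 24 (protocol 10.1). Early leavers have a termination visit (9.4). Serious events are collected for 30 days after the last dose, and related serious events after that (section 15).

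SAP 9.1 contains a second counting rule: repeat events in one patient are all counted, over the total population. Immunogenicity is listed as "Antibody dosages, baseline and at weeks 12 and 24" (SAP 3.2.3).

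**The concern.** This is not ordinary dropout. The protocol itself makes the length of adverse event follow-up depend on efficacy, in a trial that asks whether two epoetins perform alike. A patient withdrawn at week 12 stays in the 24-week denominator but cannot contribute a non-serious event that starts after the termination visit. The 24-week percentage therefore mixes patients observed for 24 weeks with patients observed for 12 or fewer. The chi-square test in protocol 16.6 compares these proportions as if follow-up were equal. If one product produces more non-response, its arm accrues less observed time, and part of any safety disadvantage can be hidden.

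**Working it through.** **Inputs.** The documents state no adverse event, non-response or transfusion rate, so there is no safety figure to reproduce. The planned 120 patients concern haemoglobin and do not bear on this point. The rates below are assumptions: q, the 12-week patient-level risk, 20–70%; d, the share withdrawn at week 12 with later events not collected, 10–40%. From SAP section 5: 43 patients enrolled, 23 and 20.

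**Formula (constant hazard).**
- Full-follow-up 24-week risk: 1 − (1−q)².
- Crude figure under SAP 9.1: (1−d)[1 − (1−q)²] + d·q.
- Shortfall: d·[1 − (1−q)² − q] = d·q·(1−q), never negative.

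**One arm.**

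| q | full risk | crude, d=10% | crude, d=30% | crude, d=40% |
|---|---|---|---|---|
| 20% | 36.0 | 34.4 | 31.2 | 29.6 |
| 30% | 51.0 | 48.9 | 44.7 | 42.6 |
| 50% | 75.0 | 72.5 | 67.5 | 65.0 |
| 70% | 91.0 | 88.9 | 84.7 | 82.6 |

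The shortfall runs from 1.6 points (0.1 × 0.2 × 0.8) to 10.0 (0.4 × 0.5 × 0.5). Adding 5% transfused at week 6, with q=30% and d=30%, lowers 44.7% to 43.0%.

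**Two arms, same hazard.** The spurious difference is (d₁−d₂)·q·(1−q). With 30% against 10% withdrawn and q=30%: 0.2 × 0.21 = 4.2 points (44.7% against 48.9%); over the q range, 3.2 to 5.0 points. With d₁=d₂ it is zero.

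**Two arms, hazard 25% higher in one.** Take a 24-week risk of 50% in the comparator and 58.0% in the other arm, with 20% and 40% withdrawn. The crude figures are 45.9% and 48.8%: a true 8.0 points appears as 2.9.

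**Higher hazard in non-responders** (q=30% in responders, 30% against 10% withdrawn).
- Twice the hazard: crude 51.0% against 51.0%; full follow-up 58.5% against 53.5%.
- Three times: crude 55.4% against 52.5%; full follow-up 62.2% against 54.7%.

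Crude stays below full-follow-up risk, but the arm with more non-response no longer looks safer.

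**Repeat-counting rule** (q=30%, constant rate). Events per 100 treated are 60.6 at d=30%, 67.8 at d=10% and 71.3 with full follow-up. All exceed the 51.0% patient-level risk, so a percentage built this way would overstate patient incidence while still losing exposure. Per 100 patient-weeks the three agree: 60.6/2,040 = 67.8/2,280 = 71.3/2,400 = 2.97%, that is, 2.97 events.

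**Enrolled sizes.** Assume 7 of 23 and 2 of 20 withdrawn at week 12, q=30%. Observed time is 7×12 + 16×24 = 468 and 2×12 + 18×24 = 456 patient-weeks. Expected patients with an event are 10.26 (44.6%) and 9.78 (48.9%).

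**The case against.** A reader might infer that the reported 24-week incidence is certainly too low and favours the less effective product. The documents do not support that. The second rule in SAP 9.1 can push the printed percentage above patient-level risk. A false advantage needs unequal withdrawal and similar hazards in responders and non-responders, and no rates are given for either.

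A reader might also infer that week-24 antibody results describe responders only and that exit samples fit no time point. That is not established. Visit 11 doubles as the end-of-study visit (protocol 12.3.6, SAP 4.4) and includes an antibody sample. Protocol 14.2.7 places that sample at week 24 or study completion, and week-12 non-responders are sampled at visit 8. What remains is a labelling question: an early-exit sample could be tabulated as week 24.

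Further points on the plan's side stand:
- Serious events are collected for 30 days after the last dose, so the model overstates their loss.
- The 12-week incidence is untouched by week-12 withdrawal; only earlier exits, such as transfusion, affect it.
- SAP 7.1 and 7.6 already show withdrawals by reason and dose by stage, though nothing links them to event incidence.
- An all-treated denominator is legitimate. Dividing by maintenance entrants compares response-selected groups, and Kaplan-Meier censoring at non-response may be informative.
- At 23 against 20, a 4-point distortion is about one patient; the standard error of a difference near 50% is √(0.25/23 + 0.25/20), about 15 points.

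These are reasons to supplement the crude measure, not to replace it. They do not make it sufficient alone.

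**Conclusion.** This is a cheap improvement, not a flaw that invalidates the safety analysis. It is established from the text that the denominator is everyone treated, that the protocol ends follow-up according to efficacy, and that no planned measure allows for unequal exposure. For patient-level incidence read as a 24-week risk, the shortfall is 1.6 to 10.0 points over the assumed ranges, with a constant hazard and no event collection after week-12 withdrawal. The between-arm effect is conditional: zero with equal withdrawal, 3.2 to 5.0 points at 30% against 10% with equal hazards, and a level or reversed observed ranking when non-responders have two or three times the hazard. The actual size in this trial cannot be known from the documents.

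**What to change.** In SAP 9.1:

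1. Keep crude all-treated incidence at 12 and 24 weeks. Add, by arm, patients with an event and events per 100 patient-weeks, and a Kaplan-Meier or cumulative incidence estimate to week 24. Show patient-weeks of exposure and withdrawals by reason alongside. For the patient-based rate, count time only to the first event: over total time the enrolled-size example gives 10.26/468 = 2.19% against 9.78/456 = 2.14%, unequal despite equal hazards.
2. Show weeks 12–24 incidence among maintenance entrants as descriptive only, labelled as a response-selected group.
3. Reconcile the two counting rules: count patients for incidence, and report event counts separately.
4. Report antibodies also as any positive post-baseline sample, including the termination-visit sample, over all patients with a post-baseline sample. Do not pool early-exit samples under the week-24 label.

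The cost is SAP wording and a few tables from data already collected. The SAP should state that censoring at non-response may be informative. Because SAP section 5 reports that interim results had been seen, the added measures must be declared as specified after the interim analysis.

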3.2 Key Protocol Information

3.2.1 Study Objectives and Endpoints

3.2.2 Study Objectives

GENERAL OBJECTIVE

Evaluate the efficacy and safety of HEMAX PFS compared with EPREX/ERYPO®, following a dose titration and maintenance scheme similar to that used in the clinical practice in Argentina.

PRIMARY OBJECTIVE:

Evaluate the efficacy of treatment with epoetin alfa through increased levels of hemoglobin (Hb) from baseline value to the mean value of the 8 to 12 weeks of treatment, comparing patients treated with HEMAX PFS versus those treated with EPREX/ ERYPO®.

Evaluate the safety through the incidence of adverse events and adverse reactions after 12 and 24 weeks of treatment, comparing patients treated with HEMAX PFS versus those treated with EPREX/ ERYPO.

SECONDARY OBJECTIVES:

Evaluate the efficacy of treatment with epoetin alfa through the percentage of responder patients (increase of Hb \geq 1g/ dl) after 12 weeks of treatment, comparing patients treated with HEMAX PFS versus those treated with EPREX/ ERYPO®.

Evaluate the percentage of transfusion requirement after 12 weeks of treatment, comparing patients treated with HEMAX PFS versus those treated with EPREX/ ERYPO®.

Evaluate the intragroup efficacy (HEMAX PFS and EPREX/ ERYPO®) of treatment with epoetin alfa through increased levels of hemoglobin from baseline in each one of the intermediate visits until the week 12 visit.

Evaluate the intragroup efficacy (HEMAX PFS and EPREX/ ERYPO®) of the change from the twice-a-week dosing during the titration phase to a weekly dosing during the maintenance phase through the variation of the hemoglobin levels from week 12 to weeks 16, 20 and 24.

In addition, at week 12 and 24 visits, an anti-erythropoietin antibody dosing will be performed to evaluate treatment immunogenicity..

EXPLORATORY OBJECTIVE

Evaluate the baseline value of hepcidin through ELISA at 12 and 24 weeks, in relation to treatment response.

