6.4 Interim Analyses

A first interim analysis will be performed after the last study patient completes the week 12 visit and the database is clean. This analysis will produce all the efficacy and safety results at week 12.

7 Summary of Study Data

All data will be listed, taking into account site, subject, treatment, and visit number. All summary tables will be structured with a column for each treatment and will be annotated with the total population size relevant to that table, including any missing observations

Descriptive statistics:

Continuous variables will be summarized using descriptive statistics: N, mean, standard deviation, median, minimum and maximum.

Categorical variables will be presented using frequencies and percentages

Inferential statistics

Inferential statistics will be performed through intergroup analysis using ANCOVA covariance analysis comparing each treatment group (patients treated with HEMAX PFS versus those treated with EPREX/ ERYPO®) or the statistical “t” Student test for independent samples considering 5% significance level can be used. An additional intragroup analysis evaluating the variations in hemoglobin (increase from baseline to the average of the visits between weeks 8 and 12) adjusted for the baseline value, using a significance level of 5% will be calculated.

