The randomization system was defined in the electronic data collection system. provided by the company Semicrol® S.L., Santander, Spain.

The Sponsor chose an electronic data capture (EDC) system (electronic CRF). The company Semicrol® (Santander, Spain) provided the service. The Sponsor granted Access to the system to all the PIs and to all the staff selected.

Statistical analysis will be performed with SPSS (Statistical Package for Social Sciences) software² or equivalent, such as the R Core Team Program (2020)³

12 Summary of Changes to the Protocol

Two general amendments, that were applicable to all the participating centers, were made.

Amendment #1 added two additional dosage forms of the study product (pre-filled syringes x 1000 and 3000 IU) and introduced some changes at the requirement of one of the Ethics Committees, which had been extended to all the centers. These modifications included a change regarding the Pregnancy tests in urine by the HCG beta sub-unit determination in blood, additional information about statistical tests and the descriptive statistics to be used, among others, were also included.

Amendment #2 added Paraguay and Uruguay as countries that might take part of the study, potentially.

13 References

¹ Schulz KF, Altman DG, Moher D; CONSORT Group. CONSORT 2010 statement: updated guidelines for reporting parallel group randomized trials. *Ann Intern Med.* 2010 Jun 1;152(11):726-32. doi: 10.7326/0003-4819-152-11-201006010-00232. Epub 2010 Mar 24. PMID: 20335313.

² IBM SPSS version 25.0

³ R Core Team (2020). R: A language and environment for statistical computing. R Foundation for Statistical Computing, Vienna, Austria. URL <https://www.R-project.org/>.

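### SAP 9.1 defines adverse-event incidence in two incompatible ways, and the protocol's chi-square comparison of the arms is not carried into the SAP

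*SAP*

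**What the plan says.** SAP 3.2.2 lists this under the primary objective: "Evaluate the safety through the incidence of adverse events and adverse reactions after 12 and 24 weeks of treatment", compared between arms. Protocol 16.6 calls it the primary safety objective.

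On counting, SAP 9.1 makes three statements:

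- **Rule 1.** "The Tables will present the number of patients for which events occurred, and the incidence rate, expressed as a percentage", taken over the patients in what the section calls the safety FAS. Protocol 16.6 has this rule and no other.
- **Rule 2.** For incidence and any sub-classification of it, "each subject will be counted all the times a repetitions of adverse events will be occurred and the denominator will be the total population size".
- **A further display** by system and arm, which sets the number of events against the number of affected patients and calls the result a frequency.

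SAP section 7 gives each treatment its own column and has each table "annotated with the total population size relevant to that table".

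On testing, Protocol 16.6 plans descriptive statistics and adds that a "x2 test will be performed to compare the incidence of adverse events and adverse reactions" between the arms. SAP 9.1 says that "descriptive statistics will be performed mainly to evaluate the incidence of adverse events and adverse reactions after 12 and 24 weeks of treatment", and the sentence ends there. The between-group methods named in SAP sections 7 and 8 are these: "Inferential statistics will be performed through intergroup analysis using ANCOVA covariance analysis comparing each treatment group", or a t test for independent samples. SAP section 12 says that Amendment 1 brought in "additional information about statistical tests and the descriptive statistics to be used". It mentions no removal of a test.

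**The concern.** Rules 1 and 2 claim the same name and the same scope but have different numerators: patients in one, events in the other. Nothing says which governs the primary safety comparison. Two programmers could each follow a sentence of 9.1 faithfully and report different incidences from the same data. Rule 2 printed as a percentage would be a wrong figure.

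The arms are small (23 and 20 enrolled, SAP section 5), so one patient with a recurrent event can change the apparent balance between them.

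The missing test adds to this. SAP 9.1 still announces a comparison of the arms, but the SAP names no method suited to comparing two percentages of patients.

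**Working it through.** **Inputs.** Arm sizes of 23 (HEMAX PFS) and 20 (EPREX/ERYPO) come from SAP section 5, assuming all enrolled patients were dosed. Neither document gives an adverse-event rate or a number of episodes per patient, so any such value below is assumed. There is no planned safety figure to reproduce.

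**Step 1: what each rule computes.** For an arm of N patients, A of them affected, with E events in all:

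- Rule 1 = A/N, a proportion.
- Rule 2 = E/N, a mean count per patient.
- Rule 2 / Rule 1 = (E/N)/(A/N) = E/A, the mean number of episodes per affected patient.

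With a common denominator this ratio does not depend on the event rate.

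**Step 2: numbers.**

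| Case | Rule 1 | Rule 2 |
|---|---|---|
| One of 23 affected, six episodes | 1/23 = 4.3% | 6/23 = 26.1% |
| 20% affected (assumed), mean 1.1 episodes | 20% | 22% |
| 20% affected, mean 1.5 | 20% | 30% |
| 20% affected, mean 2 | 20% | 40% |
| 10 of 23 affected, 30 events | 10/23 = 43.5% | 30/23 = 130% |

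Rule 2 passes 100% as soon as events outnumber patients: 24/23 = 104.3%, 21/20 = 105.0%.

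**Step 3: the test clause.** Set side by side, the two safety sections share the descriptive wording and only the protocol continues to a chi-square test. No test for proportions appears in the SAP text available for this review, which lacked the opening pages.

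**Step 4: what would follow if repeat counts were tested (illustrative only).** Neither document prescribes this.

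One patient with six episodes and nobody else affected is 1/23 against 0/20 when patients are counted: Fisher two-sided p = 1.0. Entered as repeat counts, 6/23 against 0/20 gives p = 0.023; five episodes would give p = 0.051.

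False-positive rates were simulated with 200,000 trials per cell, identical arms of 23 and 20, and geometric episode counts. Fisher's test was used where the smallest expected count was below 5, and uncorrected chi-square otherwise. Rejection rates on repeat counts were:

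| Affected | mean 1.1 | 1.25 | 1.5 | 2 |
|---|---|---|---|---|
| 5% | 1.3% | 3.0% | 6.7% | 15.0% |
| 10% | 3.3% | 6.4% | 12.2% | 24.0% |
| 20% | 6.3% | 11.3% | 19.9% | 33.2% |
| 30% | 8.3% | 14.5% | 24.1% | 36.0% |
| 40% | 9.6% | 17.4% | 26.9% | 33.2% |

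Counting each patient once gave 0.5% to 5.1% (3.4% at 20% affected). Trials with more events than patients in an arm cannot form a 2×2 table and were excluded: at most 5.1% of trials, except 12.5% at 30%/mean 2 and 37.1% at 40%/mean 2. If those count as non-rejections, the two cells become 36.0% × 0.875 = 31.5% and 33.2% × 0.629 = 20.9%.

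**The case against.** Four points can be made in the plan's favour.

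- **The error rates are hypothetical.** The SAP names no test of adverse-event incidence, and the protocol's chi-square sits beside the patient-based rule, where the level is held. This stands. The simulation shows only what would happen if the second counting rule met the protocol's test, and the finding does not rest on it.
- **The inflation factor needs a common denominator.** SAP 9.1 says only the total population. Over all 43 patients the six-episode example is 6/43 = 14.0%. This also stands as a qualification, but the one-column-per-treatment layout in section 7 makes the arm the natural reading, and the numerators conflict under either.
- **The damage is partly contained.** The tables must also show the number of patients with events, so a careful reader could recover the patient-based percentage. This softens the consequence without settling which percentage is printed as the incidence.
- **The missing chi-square is an omission, not a contradiction.** The SAP says its safety statistics are mainly descriptive, which does not exclude a test, and nothing revokes Protocol 16.6. Section 12 describes protocol amendments, so its silence proves little. The claim is therefore limited to this: the test is not carried over and no reason is given.

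**Conclusion.** The concern holds. SAP 9.1 gives two incompatible definitions of adverse-event incidence, a quantity named under the primary objective. The second is a mean count that can exceed 100%. With the arm as denominator and all 23 and 20 enrolled patients dosed, it overstates the first by the mean number of episodes per affected patient: 26.1% against 4.3% in the six-episode example. The protocol's chi-square comparison is absent from the SAP text available, and the tests the SAP does name do not suit percentages of patients.

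Two labelling points are lesser. The SAP does not define safety FAS, which is probably the same set as its Safety Population. The events-and-affected-patients display may simply be two counts.

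This should be fixed before the tables are programmed. It does not invalidate the trial.

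**What to change.** In SAP 9.1, replace the repeat-count sentence with wording such as:

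> Incidence counts each subject once per system organ class, once per preferred term and once overall, divided by the subjects in the Safety Population (6.2.2) of that arm; the number of events is shown in a separate column.

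Replace safety FAS with Safety Population. Label the events-and-affected-patients display as an event count and a patient count, not as incidence.

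Carry the protocol's comparison into the SAP at weeks 12 and 24, for patients with at least one adverse event and for patients with at least one adverse reaction. Use chi-square, with Fisher's exact test where an expected count is below 5. With 20 patients in the smaller arm, that happens whenever the pooled proportion is under 5/20 = 25% or above 75%. Other small-sample methods would also serve; what matters is to state one. Record the exact-test rule in section 12 as a change from the protocol. If the comparison is not to be done, give the reason there instead.

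The cost is minor SAP wording and table programming. No new data are needed.
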